8.12. Digital Reminder

The Ensemble personalized health record tool by Epividian will be used to remind participants of their injection visits and administration of other medications. This would

be using a streamlined version of Ensemble that utilizes a combination of short message service (short message service [SMS] text messages) and small web pages that are loaded from links included in SMS messages. This product architecture of combined SMS and web pages allows a participant with virtually any smart phone to use the application, whereas a full-featured smart phone app would require support for specific operating systems and devices. Use of this tool is optional, but encouraged.

9. DATA MANAGEMENT

- For this study, participant data will be entered into GSK defined eCRFs, transmitted electronically to GSK or designee and combined with data provided from other sources in a validated data system.
- Management of clinical data will be performed in accordance with applicable GSK standards and data cleaning procedures to ensure the integrity of the data, e.g., removing errors and inconsistencies in the data.
- Adverse events and concomitant medications terms will be coded using Medical Dictionary for Regulatory Activities (MedDRA) and an internal validated medication dictionary, GSKDrug.
- eCRFs (including queries and audit trails) will be retained by GSK, and copies will be sent to the investigator to maintain as the investigator copy. Participant initials will not be collected or transmitted to GSK according to GSK policy.

Please refer to [Appendix 10](#) in Section [12.10](#) for study management information during the COVID-19 pandemic.

10. STATISTICAL CONSIDERATIONS

10.1. Statistical Hypotheses

No statistical hypotheses of treatment comparisons will be conducted within this study.

10.2. Sample Size Determination

Approximately 100 participants will be enrolled into this study from the LATTE study.

10.2.1. Sample Size Sensitivity

For the primary endpoint, antiviral response which will be assessed according the proportion of participants who have HIV-1 RNA ≥ 50 c/mL at Month 12, given the sample size of 100 participants and if the observed rate is around 3% then the upper bound of the 95% CI would be 6.3% ([Table 6](#)).

Table 6 Precision in Estimation According to Sample Size and Observed Proportion with HIV-1 RNA ≥ 50 c/mL

Sample Size	Observed Proportion HIV-1 RNA ≥ 50 c/mL	Upper limit of 95% Confidence Interval †
90	2%	4.9%
100	2%	4.7%
110	2%	4.6%
90	3%	6.5%
100	3%	6.3%
110	3%	6.2%
90	4%	8.0%
100	4%	7.8%
110	4%	7.7%

† Two-sided confidence Interval calculated using the normal approximation method.

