3. OBJECTIVES AND ENDPOINTS

Objectives	Endpoints
Primary	
To demonstrate the antiviral activity of CAB LA + RPV LA every 2 months in suppressed HIV-1 infected antiretroviral therapy ART-experienced participants	Proportion of participants with HIV-RNA ≥ 50 c/mL as per food and drug administration (FDA) Snapshot algorithm at Month 12
Secondary	
To demonstrate the antiviral and immunologic activity of CAB LA + RPV LA every 2 months and oral DTG +RPV	Proportion of participants with plasma HIV-1 RNA <50 c/mL (c/mL) at Month 12

Objectives	Endpoints
once daily	
using the FDA Snapshot algorithm
 
Proportion of participants with protocol-defined confirmed virologic failure (CVF) over time
 
Proportion of participants with HIV-RNA greater than or equal to 50 c/mL as per FDA Snapshot algorithm over time
 
Absolute values and changes from Baseline in viral load and CD4+ cell counts over time

To demonstrate the safety and tolerability of CAB LA + RPV LA every 2 months and oral DTG + RPV once daily	
Incidence and severity of AEs and laboratory abnormalities over time
 
Proportion of participants who discontinue treatment due to AEs over time
 
Change from Baseline in laboratory parameters over time

To assess viral resistance in participants experiencing protocol-defined confirmed virologic failure	Incidence of treatment emergent genotypic and phenotypic resistance to CAB, RPV, and DTG + RPV
To characterize CAB and RPV concentrations and population pharmacokinetics and identify important determinants of variability	Plasma PK parameters for CAB LA and RPV LA (when evaluable, trough concentrations [C_{trough}])
To assess participant reported health-related quality of life, injection tolerability/acceptability, and treatment satisfaction.	
Change from Baseline (Day 1) in HIVDQoL at Months 6 and 12 (or Withdrawal)
 
Change from baseline (Day 1) in total “treatment satisfaction” score, and individual item scores of the HIV Treatment Satisfaction Status Questionnaire (HIVTSQs) at Months 6 and 12 (or Withdrawal)
 
Change in treatment satisfaction over time using the HIV Treatment Satisfaction Change Questionnaire HIVTSQc at Month

Objectives	Endpoints
	12 (or Withdrawal).
Exploratory	

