4. STUDY DESIGN

4.1. Overall Design

Study 209035 (POLAR) is a Phase IIb, open-label, multicenter rollover study designed to assess the antiviral activity and safety of CAB LA + RPV LA administered every 2 months in approximately 100 adult HIV-1 infected participants from the LATTE study.

Participants who fulfill eligibility requirements will be entered into the study to receive CAB LA + RPV LA Q2M or the oral DTG + RPV regimen for at least 12 months, until commercially available.

Participants currently receiving oral CAB + RPV within LATTE will enter POLAR at Day 1 and choose to either transition to Q2M administration of injectable CAB LA + RPV LA or take oral DTG + RPV daily for 12 months. Eligible participants include those originally randomized to oral CAB + RPV in the Maintenance phase and transitioned to the Extension Phase of LATTE. The first injection visit for POLAR can be performed once the most recent central lab results from LATTE are available and safety parameters have been reviewed, and the LATTE Week 312 visit (close-out visit) has been completed (or Week 324 in the event of unavoidable delays). Participants will continue to receive oral CAB + RPV as scheduled within the LATTE trial until their eligibility for POLAR can be fully evaluated and the participant has chosen the new regimen. If determined to be ineligible for POLAR or participant elects to not participate in the study those participants will be withdrawn from the LATTE study.

Participants in POLAR who successfully complete Week 300 in the LATTE study (without meeting study defined withdrawal criteria) will be given the option to receive either CAB LA + RPV LA (administered Q2M) or oral DTG + RPV daily until study intervention is either locally approved and commercially available within the local sector (including through local public/government health sectors), the participant no longer derives clinical benefit, the participant meets a protocol-defined reason for discontinuation or until development of either CAB LA + RPV LA Q2M is terminated.

Any participant who receives at least one dose of CAB LA and/or RPV LA and discontinues the CAB LA + RPV LA regimen for any reason will enter a 52-week LTFU Phase. Those participants must remain on suppressive HAART for at least 52 weeks after the last dose of CAB LA and/or RPV LA.

[figure not shown]

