The 200056 (LATTE-2) (GlaxoSmithKline Document Number [2013N168152_05](#)) clinical trial evaluated a different simplification approach and served as proof of concept for POLAR. In 200056, HIV-1 RNA suppression was induced with a three-drug antiretroviral regimen consisting of CAB + ABC/3TC FDC, and then participants switched to a two-drug two-class regimen consisting of CAB LA + RPV LA for the maintenance of HIV-1 RNA suppression. Results demonstrate that through 96 weeks on two-drug maintenance therapy, 94% (Q8W IM arm) and 87% (Q4W IM) of participants maintained virologic suppression (HIV-1 RNA <50 c/mL) compared to 84% of participants continuing oral CAB + 2 NRTIs. CAB LA + RPV LA was well tolerated through Week 96 for both the Q8W and Q4W dosing regimens, as demonstrated by a low discontinuation rate due to AEs, including injection site reaction (ISR) related AEs in either dosing arm, with no significant dose-dependent trends in safety parameters. On the basis of 200056 Week 48, and Week 96 data, Q4W and Q8W IM dosing are being progressed into Phase 3 for further clinical development, respectively. The CAB LA + RPV LA Q8W regimen is currently under evaluation in the ongoing Phase IIIb ATLAS-2M study.

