4.4. Justification for Dose

4.4.1. Long Acting Injectable for Maintenance Phase

LATTE demonstrated that a 2-drug, 2-class regimen could safely maintain virologic suppression with oral CAB and RPV, which informed CAB LA and RPV LA dose selection for the Phase 2b study 200056 (LATTE-2). LATTE-2 is currently ongoing with two dosing regimens of CAB LA + RPV LA given Q4W or Q8W. Following a 20-week Induction Phase (16 weeks of oral CAB + 2 NRTIs, 4 weeks of CAB + 2 NRTIs + oral RPV), participants who were eligible to continue into the Maintenance Phase were then randomized (2:2:1) to receive IM injections of CAB LA Q4W (800 mg Day 1 then 400 mg Q4W) or Q8W (800 mg Day 1, 600 mg Week 4, 600 mg Week 8, then 600 mg Q8W) in combination with IM RPV LA Q4W (600 mg Day 1 then 600 mg Q4W) or Q8W (900 mg Day 1, 900 mg Week 8, then 900 mg Q8W), respectively, or to continue on their triple ART regimen.

The Q4W dosing strategy was selected for further investigation in Phase 3 based on observed viral suppression, safety, and tolerability at Week 48. Both Q4W and Q8W regimens were continued throughout the Maintenance Phase of LATTE-2 as planned, and Week 96 results (Table 1) were supportive of further evaluation of the Q2M regimen in the present study. Moreover, LATTE-2 was amended to permit participants to remain on their randomized LA regimen (either Q4W or Q8W) during the Extension Phase (post Week 96), and those participants randomized to the oral comparator arm were allowed transition to either LA regimen at Week 96. Forty-four participants were transitioned from the oral comparator arm to LA treatments in the Extension Phase; 34 (77%) opted for the Q8W regimen and 10 (23%) for the Q4W regimen. Initial LA injections for these subjects were administered at Week 100.

Table 1 Summary of Study Outcomes (<50 copies/mL) at Weeks 48 and 96 – Snapshot (MSDF) Analysis (ITT-ME Population) in LATTE-2

Endpoint (Week)	Outcome	Q8W IM N=115 n (%)	Q4W IM N=115 n (%)	CAB 30 mg+ ABC/3TC N=56 n (%)	Subtotal IM N=230 n (%)
W48	Virologic Success, n (%)	106 (92)	105 (91)	50 (89)	211 (92)
	Virologic Failure, n (%)	8 (7)	1 (<1)	1 (2)	9 (4)
W96	Virologic Success, n (%)	108 (94)	100 (87)	47 (84)	208 (90)
	Virologic Failure, n (%)	5 (4)	0	1 (2)	5 (2)

[figure not shown]

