#### 7.1.2. Summary Measure

Number of subjects and percentage of participants with HIV-1 RNA ≥50 c/mL at Month 12 (defined by the US FDA snapshot algorithm) will be provided by treatment group.

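### Table 6 uses a normal-approximation interval that is too narrow at 2 to 4 events: at 3/100 the upper 95% limit is 7.8% to 8.5% by four standard methods, against the stated 6.3%

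*Protocol*

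**What the plan says.** Protocol Section 10.2.1 says that, with 100 participants, "if the observed rate is around 3% then the upper bound of the 95% CI would be 6.3" per cent. Table 6 repeats the calculation for n = 90, 100 and 110 at observed rates of 2%, 3% and 4%, and prints upper limits only. Its footnote reads "Two-sided confidence Interval calculated using the normal approximation method".

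Section 10.2 gives no other basis for the size of the study: "Approximately 100 participants will be enrolled into this study from the LATTE study". Section 10.1 plans no hypothesis test of treatment comparisons, and Section 10.4 and SAP Section 7.1 make the primary analysis descriptive.

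On what n refers to: in Section 4.1 participants "choose to either transition to Q2M administration of injectable CAB LA + RPV LA or take oral DTG + RPV daily". The primary objective in Section 3 begins "To demonstrate the antiviral activity of CAB LA + RPV LA every 2 months in suppressed HIV-1 infected", so it concerns the injectable regimen alone. SAP Section 7.1.2 says that the number and percentage "will be provided by treatment group".

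**The concern.** In a single-endpoint descriptive study the confidence interval is the inference, and Table 6 is the only place where the protocol says how precise that interval will be. The normal approximation relies on a roughly symmetric sampling distribution for the proportion. With 2 to 4 events in about 100 people the distribution is clearly skewed, and the method gives an upper limit that is too low. Because Table 6 shows only the upper limit, a reader cannot see the warning sign at the other end, a lower limit below zero.

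What is at stake is how much excess virologic failure the study would seem able to rule out. No pass/fail rule is affected.

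**Working it through.** **Inputs.** From Protocol Section 10.2.1: n = 90, 100, 110; observed rates 2%, 3%, 4%; two-sided 95%; normal approximation. From Table 1 in Protocol Section 4.4.1: 8 virologic failures in 115 on Q8W at Week 48 and 5 in 115 at Week 96.

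**1. Reproduce the plan's figure.** Upper limit = p + 1.96 × √(p(1−p)/n). At 3% and n = 100: √(0.03 × 0.97/100) = 0.01706, and 0.03 + 1.96 × 0.01706 = 0.0634, or 6.3%. All nine cells reproduce to one decimal:

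| n | 2% | 3% | 4% |
|---|---|---|---|
| 90 | 4.89 | 6.52 | 8.05 |
| 100 | 4.74 | 6.34 | 7.84 |
| 110 | 4.62 | 6.19 | 7.66 |

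**2. Lower limits by the same formula.** These are negative in seven of the nine scenarios, from −0.89% (2%, n = 90) to −0.05% (4%, n = 90). Only 4% at n = 100 (0.16%) and at n = 110 (0.34%) are positive.

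**3. Other methods at n = 100.**
- Exact (Clopper-Pearson): the 0.975 quantile of Beta(x+1, n−x). As a check, P(X ≤ 3) at p = 8.52% is 0.025.
- Jeffreys: the 0.975 quantile of Beta(x+½, n−x+½).
- Mid-P: the p that solves P(X < x) + ½P(X = x) = 0.025.
- Wilson: [p + z²/2n + z√(p(1−p)/n + z²/4n²)] / (1 + z²/n). At 3/100 this is (0.03 + 0.01921 + 0.03856)/1.03841 = 0.0845.

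| Events | Stated | Jeffreys | Mid-P | Wilson | Exact |
|---|---|---|---|---|---|
| 2 | 4.7% | 6.26% | 6.45% | 7.00% | 7.04% |
| 3 | 6.3% | 7.79% | 7.95% | 8.45% | 8.52% |
| 4 | 7.8% | 9.23% | 9.37% | 9.84% | 9.93% |

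From unrounded values, the gap to the stated method is 1.45 points (Jeffreys) to 2.17 points (exact) at 3 events. The exact gap is 2.29 points at 2 events and 2.08 at 4.

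**4. Coverage at n = 100.** Coverage is the sum of the binomial probabilities of every x whose interval contains the true rate. By the normal approximation the upper limit is 0% with 0 events, 2.95% with 1 and 4.74% with 2. So the upper limit falls below the truth as follows:
- true 2%: only when X = 0, probability 13.3%; total coverage 86.6%;
- true 3%: when X ≤ 1, probability 19.5%; total coverage 80.2%;
- true 4%: when X ≤ 1, probability 8.7%; total coverage 90.6%.

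The nominal upper-side miss rate is 2.5%. Averaged over a 201-point grid of true rates from 2% to 4%:

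| Method | Coverage | Upper-side misses | Lowest coverage on grid |
|---|---|---|---|
| Normal approximation | 88.4% | 11.2% | 79.6% |
| Jeffreys | 94.3% | 3.1% | 88.0% |
| Mid-P | 96.1% | 1.6% | 92.1% |
| Wilson | 95.8% | 0.3% | 93.5% |
| Exact | 98.1% | 0.4% | 96.4% |

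Put another way, if the true rate were 6.3%, 3 or fewer events in 100 would occur 11.8% of the time, not 2.5%.

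**5. A gauge from the protocol's own data.** Section 4.3 says the LATTE-2 "clinical trial evaluated a different simplification approach and served as proof of concept for POLAR". In its Table 1, "Summary of Study Outcomes (<50 copies/mL) at Weeks 48 and 96", Q8W virologic failure at Week 48 was 8/115 = 7.0%. By Table 6, 3/100 (upper limit 6.3%) would seem to exclude 7.0%. By all four other methods (7.79% or more) it would not. If the true rate were 8/115, 3 or fewer events in 100 would occur 7.7% of the time.

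**6. Arm size, secondary.** The documents plan no split between the regimens. Suppose, purely as an assumption, that 80 to 90 of the 100 choose injections and the observed rate stays at 3%. The exact limit, using the beta formula with 2.7 and 2.4 events, is then 8.95% at n = 90 and 9.49% at n = 80, against 8.52% at n = 100. By the protocol's own method the figures are 6.5% and 6.7%, against 6.3%. The interval method matters more than the arm size.

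**The case against.** The strongest reply is that nothing here is miscalculated. The method is disclosed, every cell is right for it, there is no hypothesis, margin or stopping rule, and enrolment is set by how many people roll over from LATTE, so Table 6 does not determine n. The intervals finally reported will come from observed data in SAP Figures 2.01 and 2.02. All of that stands, and it limits the consequence. It does not make the stated precision right: a 95% limit that the true rate exceeds 9% to 19% of the time is not a 95% limit in any useful sense.

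The second reply is that exact and Wilson limits over-correct on the upper side (misses of 0.4% and 0.3% against a nominal 2.5%) and that 80.2% is close to the lowest point of an oscillating coverage curve. Both are true. Mid-P and Jeffreys are closer to nominal on that side, and against those two the shortfall at 3/100 is about 1.4 to 1.6 points. Average coverage by the plan's method is still only 88.4%.

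Third, the protocol makes no comparison with 7.0%. The LATTE-2 figure is itself an estimate (exact 95% interval about 3.1% to 13.2%), its population and loading schedule differ, and at Week 96 failure was 5/115 = 4.3%, which lies below both 6.3% and 8.5%. The comparison therefore shows only how large the gap is and supports no inference about efficacy.

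Fourth, Section 4.1 speaks of assessing the injectable regimen in about 100 participants, and Table 6 already has n = 90 rows. That softens the arm-size point, but Section 10.2 gives the same 100 as total enrolment, and the two readings are not reconciled.

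**Conclusion.** The concern holds. The 6.3% is a correct normal-approximation limit, but it overstates the precision of the primary endpoint by about 1.4 to 2.2 percentage points at 3 events in 100, and by similar amounts at 2 and 4. The direction is the same under all four alternative methods, so it does not depend on preferring a conservative one. The result assumes independent binomial outcomes and true rates in the 2% to 4% range that Table 6 itself uses. The arm-size point adds a smaller loss of precision whose size rests on an assumed split. This should be fixed because it is the protocol's only precision statement, but no decision rule or participant number turns on it.

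**What to change.** Restate Table 6 and the sentence above it with exact or Wilson limits, tabulated by event count, and name the method. Exact upper 95% limits:

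| n | 2 events | 3 events | 4 events |
|---|---|---|---|
| 80 | 8.74% | 10.57% | 12.31% |
| 90 | 7.80% | 9.43% | 10.99% |
| 100 | 7.04% | 8.52% | 9.93% |
| 110 | 6.41% | 7.76% | 9.05% |

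The sentence would then give 8.5% at 3/100. Jeffreys (7.8%) would also be defensible if named. Whole event counts avoid the fractional events implied by rows such as 2% of 90, but the observed percentage should be printed beside each count, since 3/90 is 3.3% and does not correspond to the present 3% row. State that n means the CAB LA + RPV LA arm.

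Optionally, name the same method for the 95% intervals in SAP Figures 2.01 and 2.02, whose entries in the list of displays name none. The normal approximation would give 0% to 0% at any visit with no events.

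The cost is one table and one sentence, as a minor text change at the next protocol amendment. It needs no more participants or data and changes no decision rule. The stated precision becomes less favourable.

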10.3. Populations for Analyses

For purposes of analysis, the following populations are defined:

Population	Description
Enrolled	All participants who sign the informed consent form (ICF)
Safety	All participants who take at least 1 dose of study intervention. Participants will be analyzed according to the intervention they actually received. This population will be used for all summaries unless otherwise specified.

10.4. Statistical Analyses

Endpoint	Statistical Analysis Methods
Primary	Descriptive summaries of the proportion of participants with plasma HIV-1 RNA ≥ 50 c/mL as per FDA Snapshot algorithm at Month 12.
Secondary	
Descriptive summaries of the following secondary efficacy endpoints will be produced:
 
 Proportion of participants with plasma HIV-1 RNA < 50 c/mL (c/mL) at Month 12 using the FDA Snapshot algorithm (Missing, Switch or Discontinuation = Failure, Intent-to-Treat Exposed [ITT-E] population) Proportion of participants with protocol-defined confirmed virologic failure (CVF) through over time Proportion of participants with HIV-RNA greater than or equal to 50 c/mL as per FDA Snapshot algorithm overtime Absolute values and changes from Baseline in viral load and CD4+ cell counts

Endpoint	Statistical Analysis Methods
	over time
Exploratory	Will be described in the reporting and analysis plan (RAP)

10.4.1. Safety Analyses

All safety analyses will be performed on the Safety Population.

Endpoint	Statistical Analysis Methods
Secondary	Descriptive summaries of the following safety endpoints will be produced: Incidence and severity of AEs and laboratory abnormalities over time Proportion of participants who discontinue treatment due to AEs over time Change from Baseline in laboratory parameters over time
Exploratory	Will be described in the reporting and analysis plan

10.4.2. Other Analyses

PK, viral resistance, health outcomes and digital assistance program analyses will be described in the reporting and analysis plan. The population PK analysis and pharmacodynamic analyses will be presented separately from the main clinical study report (CSR).

10.5. Interim Analyses

The Reporting and Analysis Plan will describe the planned interim analyses in greater detail.

12. SUPPORTING DOCUMENTATION AND OPERATIONAL CONSIDERATIONS

12.1. Appendix 1: Abbreviations and Trademarks

3TC	Lamivudine, EPIVIR
ABC	Abacavir, ZIAGEN
ABC/3TC	Abacavir/lamivudine, EPZICOM, KIVEXA
ABC/DTG/3TC	Abacavir/dolutegravir/lamivudine, TRIUMEQ
ADR	Adverse drug reaction
AE	Adverse event
AIDS	Acquired immunodeficiency syndrome
ALT	Alanine aminotransferase
Anti-HBc	Hepatitis B core Antibody
Anti-HBs	Hepatitis B surface antibody
Anti-HbsAg	Antibodies against Hepatitis B surface Antigen
APAP	N-acetyl-para-aminophenol
ARV	Antiretroviral
ART	Antiretroviral therapy
AST	Aspartate aminotransferase
AUC	Area under the curve
AUC(0- τ)	Area under the concentration curve from 0 hours to the time of next dosing
BMI	Body Mass Index
BP	Blood Pressure
BUN	Blood Urea Nitrogen
CAB	Cabotegravir
CABG	Coronary artery bypass grafting
CAB LA	Cabotegravir long-acting
c/mL	Copies/milliliter
cART	Combination antiretroviral therapy
CHORUS	Clinical Health Outcomes Reporting and Utilization Service
CD4	Cluster of Differentiation 4
CD8	Cluster of Differentiation 8
CDC	Centers for Disease Control and Prevention
CKD-EPI	Chronic Kidney Disease Epidemiology Collaboration
C _{max}	Maximum concentration
CNS	Central Nervous System
CO ₂	Carbon Dioxide
ConART	Concomitant Antiretroviral Therapy
COVID-19	Coronavirus Disease 2019
CPK	Serum creatine phosphokinase
CSR	Clinical Study Report
C _{trough}	Trough Concentrations
CI	Confidence interval
CIOMS	Council for International Organizations of Medical Sciences

C _τ	Trough Concentration
CV	Cardiovascular
CVF	Confirmed Virologic Failure
DAIDS	Division of Acquired Immunodeficiency Syndrome
DDI	Drug-Drug Interaction
DILI	Drug induced liver injury
dL	Deciliter
DNA	Deoxyribonucleic acid
DRE	Disease-Related Events
DRESS	Drug Reaction with Eosinophilia and Systemic Symptoms
DTG	Dolutegravir, TIVICAY
DVT	Deep vein thrombosis
ECG	Electrocardiogram
eCRF	Electronic case report form
EFV	Efavirenz
EFV/TDF/FTC	Efavirenz/tenofovir disoproxil fumarate/emtricitabine
GFR	Glomerular filtration rate
EVG	Elvitegravir
FDA	Food and Drug Administration
FDC	Fixed-dose combination
FRP	Females Of Reproductive Potential
FSH	Follicle Stimulating Hormone
GCP	Good Clinical Practice
GCSP	Global Clinical Safety and Pharmacovigilance
GI	Gastrointestinal
GSK	GlaxoSmithKline
HAART	Highly active antiretroviral therapy
HbsAg	Hepatitis B surface Antigen
HBV	Hepatitis B virus
HCG	human chorionic gonadotrophin
HCV	Hepatitis C virus
HDL	High density lipoprotein
HDPE	High density polyethylene
HIPPA	Health Insurance Portability and Accountability Act
HIV	Human immunodeficiency virus
HIVDQoL	HIV Dependent Quality of Life
HIV TSQ	HIV treatment satisfaction questionnaire
HIV TSQ(c)	HIV treatment satisfaction questionnaire change version
HIV TSQ(s)	HIV treatment satisfaction questionnaire status version
HLA	Human leukocyte antigen
HR	Heart Rate
HRT	Hormone Replacement Therapy
HSR	Hypersensitivity reaction
IB	Investigator's Brochure
ICH	International Conference on Harmonisation
IDMC	Independent Data Monitoring Committee

IEC	Independent Ethics Committee
IgG	Immunoglobulin G
IgM	Immunoglobulin M
IM	Intramuscular
INH	Isonicotinylhydrazid
INI	Integrase inhibitor
INR	International normalized ratio
IP	Investigational Product
IRB	Institutional Review Board
ITT-ME	Intent-to-Treat Maintenance Exposed
ITT-E	Intent-to-treat exposed
IUD	Intrauterine device
IUS	Intrauterine hormone-releasing system
ISR	Injection Site Reaction
IV	Intravenous
Kg	Kilogram
LA	Long Acting
LATTE	Long Acting anTiretroviral Treatment Enabling Study
LATTE-2	Long Acting anTiretroviral Treatment Enabling Study - 2
LDH	Lactate Dehydrogenase
LDL	Low density lipoprotein
LLOD	Lower Limit Of Detection
LOC	Local Operating Company
LTFU	Long-Term Follow-UP
MCV	Mean corpuscular volume
MedDRA	Medical dictionary for regulatory activities
meq	Milliequivalence
MDL	Medicines Development Leader
Mg	Milligram
Mg/dL	Milligram
mmol	Millimolar
MSDS	Material Safety Data Sheet
msec	Milliseconds
µg	Microgram
ng	Nanogram
NOAEL	No-Observed-Adverse-Effect-Level
NNRTI	Non-Nucleoside reverse transcriptase inhibitor
NRTI	Nucleoside reverse transcriptase inhibitor
NVP	Nevirapine
OCT-2	Organic cation transporter
PA-IC90	Protein-Adjusted 90% Inhibitory Concentration
PBMCs	Peripheral Blood Mononuclear Cells
PDVF	Protocol-defined virologic failure
PI	Protease inhibitor
PK	Pharmacokinetic
PO	Per-oral

PP	Per-protocol
PPL	Project Physician Leader
PPN	Pre- and Postnatal
PrEP	Pre-exposure prophylaxis
PRO	Protease
PRTD	Proximal Renal Tubule Dysfunction
PSRAE	Possible suicidality-related adverse event
PT	Prothrombin Time
PTS-DMPK	Platform Technology and Science - Drug Metabolism and Pharmacokinetics
PTT	Partial Thromboplastin Time
PTCA	Percutaneous transluminal coronary angioplasty
PUD	Peptic Ulcer Disease
QTc	Corrected QT interval
Q2M	Every 2 months
Q8W	Every 8 weeks
Q4W	Every 4 weeks
RAP	Reporting and Analysis Plan
RBC	Red blood cell
RNA	Ribonucleic acid
RPR	Rapid plasma reagin
RPV	Rilpivirine, Edurant
RPV LA	Rilpivirine long-acting
RT	Reverse transcriptase
SAE	Serious adverse event
SJS	Stevens-Johnson syndrome
SMS	Short message service
SOC	Standard of Care
SPM	Study Procedures Manual
STR	Single tablet regimen
SVF	Suspected Virologic Failure
TDP	Torsade des Pointes
TEN	Toxic epidermal necrolysis
TMC278	Tibotec Medicinal Compound 278
UDP	UDP-glucuronosyltransferase
ULN	Upper limit of normal
US	United States
VSLC	ViiV Safety and Labeling Committee
WBC	White blood cell
WOCBP	Woman of Childbearing Potential

Trademark Information

Trademarks of ViiV Healthcare
EPZICOM/KIVEXA
TIVICAY
TRIUMEQ
TRIZIVIR
ZIAGEN

Trademarks not owned by ViiV Healthcare
Edurant
Genosure
InForm
MedDRA
PhenoSense

